Protocol Changes

Changes made from version 2 (published May 14, 2019) to version 3 (December 3, 2020)

- Two new investigators added (title page):
[name], Copenhagen Emergency Medical Services, Ballerup, Denmark
[name], National Institute of Public Health, University of Southern Denmark, Copenhagen, Denmark
One investigator removed (title page):
[name], Copenhagen Emergency Medical Services, Ballerup, Denmark
- Power calculation changed. Baseline survival is increased from 12% to 15% based on data from 2018 from the Danish Cardiac Arrest Registry that has been published recently. Effect estimate for stratum 1 has been decreased from 35% to 25%. The new power calculation, including these new data, results in a sample size of 536 patient for both stratum 1 and 2. Since we are expecting 64% to be true OHCA and a citizen responder only arriving before EMS in 40% of the cases, we will include 2094 patients in stratum 1 and 2094 patients in stratum 2 (section 5.2)
- Length of study changed from 4 years to up to 8 years, and total included patients changed to approximately 4200 because of changes in power calculation (multiple sections)
- New wording for the approval from the Ethics Committee and addition of add-on approvals from the Danish Patient Safety Authority for data collection in 2019 and 2020 (Scientific summary and section 8)
- Secondary outcome. Neurological intact survival will be assessed at hospital discharge through patient's charts, not at 30 days. This is changed in multiple sections and a new data source has been added to section 4.12
- Safety outcome. Psychological impact will not be assessed at 4 weeks but assessed through a survey sent out 90 minutes after activation. Non-responders will be followed-up by phone call, text message or e-mail.
- Stratum 3 will not be included in analyses since this stratum is assumed to be very small.
- One subgroup has been deleted (arrival of citizen responders prior to EMS, since this is not assessable for the control group). The subgroup assessing OHCAs in public and residential settings has been divided up into two separate groups.
- The wording *heart runner* has been changed to *citizen responder* throughout the protocol

- Corrections of grammar and minor typing errors throughout the protocol

Statistical Analysis Plan

1. Outcome Measures

Primary outcome:

1. 30-day survival in OHCA patients included in the HeartRunner trial.

Secondary outcomes:

1. Bystander defibrillation prior to EMS arrival
2. Bystander cardiopulmonary resuscitation prior to EMS arrival
3. Return of spontaneous circulation at hospital arrival
4. Neurological intact survival at hospital discharge (cerebral performance category score of 1-2)¹
5. 1-year survival

For safety outcomes the secondary outcomes are:

1. Physical injuries or accidents among activated citizen responders
2. Psychological stress or anxiety among activated citizen responders

Physical injuries and psychological stress will be assessed through an electronic survey sent out 90 minutes after activation. Non-responders will be followed up by phone call, text message or e-mail.

2. Power calculations

There was an overall survival of approximately 15% in 2018 in Denmark. Based on prior studies from Stockholm and Holland time to arrival of bystanders decreased by 2.5 minutes with introduction of activated lay persons. Experiences from Sweden have shown that volunteer citizen responders can be recruited and arrive before all dispatched units in 25% of the cases.^{2,3}

This is a superiority trial and sample size and power calculations are based on an assumed effect size using a binary outcome (30-day survival). Data from Danish OHCA cases without introduction of a HeartRunner program showed a decreased chance of survival with increasing EMS response times (30-day survival for all OHCA cases were 12%, 8%, and 4% for EMS response times of <5 minutes, 5-10 minutes, and >10 minutes, respectively).⁴ Similarly, the chance of having a shockable heart rhythm (ventricular fibrillation/pulseless ventricular tachycardia) decreased from 50% within 5 minutes, 30% within 5-10 minutes, and below 20% for EMS response times above 10 minutes.⁴

Estimated 30-day survival chances according to citizen responder response times are: 25% within 3 minutes, 25% within 3-9 minutes, and 4% after 9 minutes.

Power calculations estimated by Fisher's exact test according to time strata are then (using a power (1-beta) of 0.80 and a significance level (alpha, two-sided test) of 0.05): <3 minutes: 536 patients (increase from 15 to 25%) and 3-9 minutes (increase from 15 to 25%): 536 patients.

Data from the pilot study showed approximately 64% of suspected OHCA were real OHCA. Further, in approximately 40% of cases for which the HeartRunner system was activated, at least 1 citizen responder arrived prior to EMS. It is thus necessary to account for these conditions when calculating power for this study. Thus, for group 1 and 2, 536 cases of true OHCA would be identified among 838 cases of suspected OHCA. To achieve at least 838 suspected OHCA where at least one activated citizen responder arrived prior to EMS, it would require 2094 suspected OHCA. Thus, in total, 2094 suspected cardiac arrests in stratum 1 and in stratum 2 are estimated to be included in the study. Power calculations were performed using the procedure Power (with the twosamplefreq statement based on Fisher's exact test) in SAS version 9.4 (SAS Institute, Cary, NC, USA).

The study is powered to independently address primary outcomes in the 2 time strata according to expected time from activation to arrival of a citizen responder who can assist with resuscitation: <3 minutes (stratum 1) and 3-9 minutes (stratum 2).

3. Statistical Analysis

Eligibility, allocation, inclusion and exclusion are displayed in a trial diagram (Figure 1) and described in section 4 Study Methods in the study protocol version 3. Analysis will be performed following an intention-to-treat principle (patients for whom the HeartRunner system was activated vs. not activated), except for cases excluded as described in subsection 4.6. Baseline characteristics will be summarized as means and standard deviations, medians and interquartile ranges, or frequencies (number, percentages). The following baseline characteristics will be reported for both groups (intervention vs. control): median age, proportion of male patients, proportion with an initial shockable heart rhythm, proportion of witnessed OHCA, proportion of OHCA at home, time of day (8 a.m.-4 p.m., 4 p.m. -12 a.m., 12 a.m.- 8 a.m.), median EMS response time (defined as time from call to vehicle stop at scene), time difference between dispatch of EMS and dispatch of citizen responders, defibrillation performed by EMS, and median distance to nearest AED from the OHCA location.

The primary outcome (30-day survival) will be reported as proportion of patients surviving 30 days for the intervention and control group. Fisher's exact test will be used to test whether activating the citizen responder system can improve 30-day survival. Results will be presented as a relative risk (RR) with a corresponding 95% confidence interval (95% CI) and a risk difference (RD) with a corresponding 95%

confidence interval (95% CI), Table 1. Survival during the first 30 days will be presented using cumulative survival.²

Analysis of the secondary outcomes (bystander defibrillation, bystander cardiopulmonary resuscitation, return of spontaneous circulation on hospital arrival, and neurological intact survival (cerebral performance category score of 1-2 at hospital discharge), and 1-year survival) will be reported as proportions and compared within intervention groups using Fischer's exact test as described above for the primary outcome.

All tests will be performed independently in the 2 time stratum of the study. As a secondary analysis, data from stratum 1 and 2 will be combined. The combined analysis will be performed using a logistic regression with intervention (yes, no) and time (<3 and 3-9) as fixed effects. An exact test of the effect of the intervention will be performed. Stratum 3 will be described but not statistically analysed since this group is expected to be very small.

The safety outcomes physical injuries and psychological distress and anxiety among the activated citizen responders will be presented by frequency distributions (number, percentages).

Outcome	Intervention N_{OHCA}/N_{survival} (%)	Control N_{OHCA}/N_{survival} (%)	RR (95% CI)	RD (95% CI)	p-value
Primary outcome: 30-day survival					
<3 min					
3-9 min					
>9 min					
Secondary outcome: Bystander defibrillation prior to EMS arrival					
<3 min					
3-9 min					
>9 min					
....					

Table 1. Primary and secondary outcome. RR, relative risk; RD, risk difference; CI, confidence interval; OHCA, out-of-hospital cardiac arrest; EMS, emergency medical services

4. Additional Statistical Analysis

In addition to the standard frequentist analysis, to aid interpretation of the results, we will also perform a Bayesian analysis. If the assumptions underlying the design of the trial are found to be substantially incorrect (for example, the proportion of survivors may be lower than was anticipated), the precision of the trial's results may be reduced, which would reduce the chance of any treatment difference reaching the conventional threshold for statistical significance. In this situation, interpretation of the results by clinicians

and decisionmakers will be helped by producing a quantitative summary of the probability that activation of HeartRunners is beneficial, taking into account existing evidence and the trial's results.

Bayesian analyses will be performed to estimate the posterior distribution of the OR and the corresponding 95% credible intervals for each outcome stratified by time stratum.

The Bayesian analysis will model each outcome (primary and secondary) using betabinomial distributions (as the outcomes are binary). The posterior distribution of the odds ratio for each outcome will be estimated. Analyses will use separate priors for the intervention and comparison groups. For the comparison group, a weakly informative prior will be used. For the intervention group, an informative prior based on data from previous studies will be used. Sensitivity analyses will examine the effect of changing the prior distributions.

5. Subgroup Analysis

Since time from cardiac arrest to defibrillation is the most powerful determinant of survival, there may be heterogeneity of the intervention effect between subgroups that inherently differ in time from cardiac arrest to citizen responder intervention due to practical circumstances.⁵ Differences in the primary outcome are therefore anticipated in the following groups:

1. Witnessed OHCA defined as someone (not EMS) sees or hears the person collapse with a cardiac arrest.
2. According to ambulance response time (< 5 minutes, 5-10 minutes, >10 minutes) defined as time from emergency call to arrival of EMS at the OHCA location, not at the patient's side.
4. Cardiac arrests occurring in public settings. Public OHCA will be defined as a cardiac arrest occurring in public buildings, sport facilities, airports, work/office buildings, outdoor locations, and in public transport.
5. Cardiac arrest in residential setting. Residential OHCA will be defined as a cardiac arrest occurring in private homes.
6. Distance from OHCA to nearest AED (0-250m, 251-500m, 501-1000m, >1000m). Distances will be calculated as straight-line.

A test for interaction in subgroups in relation to the intervention effect (citizen responder activation) will be performed for the primary outcome for the above-mentioned groups. This study is not powered to detect differences in primary outcome between intervention and control arm in the subgroups.

To test whether the effect of the intervention (citizen responder activation) differ significantly between the subgroups for the primary outcome (30-day survival), the interaction between the intervention and subgroup (subgroup-intervention interaction) will be tested. A logistic regression with intervention (yes, no), subgroup and the interaction between intervention and subgroup will be used. The analysis will include stratum 1 (<3min) and stratum 2 (3-9 min) and stratum will therefore be included as fixed effects. An exact test of the subgroup-intervention interaction effect will be performed. Results will be presented as proportion of patients surviving 30 days in the intervention and comparison groups, relative risk (RR) with a corresponding 95% confidence interval (95% CI) and a risk difference (RD) with a corresponding 95% confidence interval (95% CI), Table 1.

6. Statistical stopping criteria

A Data Safety and Monitoring Board with statistical, cardiological and prehospital expertise will follow the study. Formal interim analyses are not planned. This committee is composed of members otherwise independent of the study. They can recommend the steering committee to discontinue the study, but it is the only body which during the course of the study received unblinded results grouped by treatment. The Safety Committee and Monitoring Board will form its own guidelines. The major events to be considered by the safety committee are survival rates (effect) and serious physical injuries or psychological stress among citizen responders (safety). The primary tracking of safety uses a research computer linked directly to the HeartRunner mission server. Using this system, responses can be tracked continuously, and reports can be prepared for the study Data Safety and Monitoring Board. Further, events that come to the attention of study staff and which are not covered by tracking of citizen responder responses and which are either fatal, life threatening, causes hospitalization or lengthening of hospitalization, results in significant or lasting disability or leads to a congenital defect will be reported as well.

7. References

1. Jennett B and Bond M. Assessment of outcome after severe brain damage. *Lancet*. 1975;1:480-4.

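### The 2094 suspected arrests per stratum are sized for cases reached before EMS, but the primary test compares all activated with all non-activated cases, so the claimed 80% power does not follow

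*SAP*

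**What the plan says.** SAP section 2 (Power calculations) links survival to how quickly a citizen responder gets there: "Estimated 30-day survival chances according to citizen responder response times are: 25% within 3 minutes, 25% within 3-9 minutes". With Fisher's exact test, two-sided alpha 0.05 and power 0.80, it gives "<3 minutes: 536 patients (increase from 15 to 25%) and 3-9 minutes (increase from 15 to 25%): 536 patients".

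Two pilot figures then inflate this number. About 64% of suspected arrests were real, and "in approximately 40% of cases for which the HeartRunner system was activated, at least 1 citizen responder arrived prior to EMS". The first takes 536 to 838. The second takes 838 to 2094: "To achieve at least 838 suspected OHCA where at least one activated citizen responder arrived prior to EMS, it would require 2094 suspected OHCA". The section concludes: "The study is powered to independently address primary outcomes in the 2 time strata".

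SAP section 3 (Statistical Analysis) defines the primary comparison by intention to treat, "patients for whom the HeartRunner system was activated vs. not activated", apart from exclusions under subsection 4.6 of the protocol. Fisher's exact test is applied separately in each stratum. Pooling is secondary: "As a secondary analysis, data from stratum 1 and 2 will be combined". The Protocol Changes list for version 3 records that one subgroup was dropped: "arrival of citizen responders prior to EMS, since this is not assessable for the control group".

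**The concern.** The two inflation steps are different in kind. Suspected arrests that prove not to be arrests can be removed from both arms, so dividing by 0.64 is sound. Arrests that no responder reached before EMS cannot be removed. They remain in the activated arm under intention to treat, and their counterparts among controls cannot be identified, as the Protocol Changes list acknowledges.

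Dividing by 0.40 therefore secures 536 arrests of the reached type within a larger group, while the test uses the whole group. If the benefit is confined to reached cases, the other 60% shrink the difference between arms. Dividing by 0.40 once does not pay for that, because required sample size grows roughly with the square of the dilution. If instead the 25% was meant for the whole activated arm, the 0.40 step has no purpose.

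The power for the primary outcome in each stratum is at stake. A reader told that each stratum has 80% power could take a null result as evidence against benefit, when the test may have had about an even chance of detecting the assumed gain.

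**Working it through.** **Inputs from SAP section 2:** control survival 15%; survival with a responder 25%; two-sided alpha 0.05; power 0.80; 64% of suspected arrests real; 40% of activations with a responder there before EMS; 2094 suspected arrests per stratum.

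**Assumed, not stated in the documents reviewed:** 1:1 allocation; no deduction for subsection 4.6 exclusions.

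**Method.** Exact power is the sum, over all pairs of survivor counts in the two arms, of their binomial probabilities wherever the two-sided Fisher p-value is at most 0.05.

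**Step 1: reproduce the plan's figures.**
- 268 per arm, 15% versus 25%: power 0.802. So 536 is the total for both arms.
- 536 / 0.64 = 837.5, rounded to 838.
- 837.5 / 0.40 = 2093.75, rounded to 2094.

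**Step 2: numbers available to the primary test.** 2094 × 0.64 = about 1340 true arrests per stratum, or 670 per arm.

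**Step 3: the intention-to-treat contrast if only reached cases gain.** Activated arm: 0.40 × 25% + 0.60 × 15% = 19%. The contrast is 15% versus 19%.

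**Step 4: power at 670 per arm, control 15%.** Inputs are varied one at a time from the base case.

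| Assumption | Activated-arm survival | Power |
|---|---|---|
| Base case: 40% reached, gain only in them, 15% baseline for all | 19% | 0.468 |
| Unreached cases gain 1, 2 or 3 points (19 + 0.6 × gain) | 19.6%, 20.2%, 20.8% | 0.578, 0.682, 0.772 |
| Reached cases attain 25% from a baseline b of 18%, 12%, 10% or 8%, control average held at 15% (15 + 0.4 × (25 − b)) | 17.8%, 20.2%, 21.0%, 21.8% | 0.258, 0.682, 0.799, 0.884 |
| Share reached 30%, 50% or 60% (15 + share × 10) | 18%, 20%, 21% | 0.290, 0.649, 0.799 |
| Whole activated arm attains 25% | 25% | 0.995 |

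So 80% power at 2094 needs about 21% survival in the whole activated arm.

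**Step 5: sensitivity of the base case.** With 10% of cases excluded (603 per arm), power is 0.427. With 2:1 allocation it is 0.43 to 0.45.

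**Step 6: why one division by 0.40 is too little.** The difference falls from 10 points to 4, a factor of 2.5, and 2.5² = 6.25. The variance is somewhat lower at 15% versus 19%, which offsets part of this. By enumeration, 80% power needs about 1430 per arm (0.800; 1425 gives 0.7985). That is 2860 true arrests, and 2860 / 0.64 = about 4470 suspected arrests per stratum. The ratio is 2860 / 536 = 5.3, where the plan used 1 / 0.40 = 2.5.

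**Step 7: the planned combined analysis.** With 1340 per arm and 15% versus 19% in both strata, unstratified Fisher power is 0.773. A stratified exact conditional test, the same form as the planned exact logistic regression, gives 0.771 in 40,000 simulated trials.

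**The case against.** The best counter-argument is that 47% is one scenario which the documents do not fix. It needs four things at once: no gain in unreached cases, the same 15% baseline in reached cases, 40% reached in each stratum, and equal allocation.

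Two of these can be challenged from section 2 itself. It reports survival of 12%, 8% and 4% as EMS response time lengthens. Cases where a responder beats EMS plausibly have longer EMS times, and so a lower baseline and a larger gain if they attain 25%. And the 40% is a single pilot figure for all activations, while the strata are defined by expected responder arrival time, so the share reached may well be higher in stratum 1. Moderate departures combine: 50% reached with a 12% baseline gives 15 + 0.5 × (25 − 12) = 21.5% and power of about 86%.

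Subsection 4.6 is not in the text reviewed, and its exclusions could change the share reached. The plan also provides confidence intervals, a combined analysis, and a Bayesian analysis meant for the case where design assumptions fail. Nothing here affects type I error or the validity of the estimates.

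These points stand as limits on the size of the shortfall, and they cut both ways: 30% reached gives 29%. They do not remove the mismatch. The plan states a rise from 15 to 25% and none of the more favourable inputs. Exclusion on arrival before EMS in both arms is unlikely, since the protocol calls it not assessable in controls. The further analyses help interpretation but do not support a claim of power within each stratum.

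**Conclusion.** The concern holds. The arithmetic from 536 to 2094 is right, but the 0.40 step sizes a comparison that the plan does not make, and the contrast that it does make is never stated. Neither plain reading of the 25% gives 80% power at 2094 suspected arrests per stratum: about 47% if it applies to reached cases only, about 99.5% if it applies to the whole activated arm.

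The 47% rests on 670 true arrests per arm (1:1, no exclusions), 40% reached in each stratum, a 15% baseline throughout, and no gain in unreached cases. Varying one of the last three at a time moves power between 26% and 88%. That the stated power is unsupported does not depend on these choices; only the size of the gap does. Because it concerns the headline power claim for the primary outcome, it should be corrected.

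**What to change.** Restate SAP section 2 and leave the planned analyses and their order as they are.

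1. Say whether the 25% describes cases reached before EMS or the whole activated arm.
2. If reached cases, add text such as:

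> About 1340 true OHCA (670 per arm, 1:1) are expected per stratum. If survival rises from 15% to 25% only in the 40% reached before EMS, the intention-to-treat contrast is 15% vs 19% and power is about 47% per stratum. It is about 58%, 68% or 77% if unreached cases have 10%, 20% or 30% of that gain.

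   List the assumptions on baseline survival, share reached in each stratum and allocation ratio.
3. If the whole activated arm, delete the 0.40 step and state the power that results (about 99.5% at 2094).
4. Change the sentence claiming independent power in the two strata to match.
5. Give the approximate power of the combined analysis (about 77% at 15% vs 19% in both strata), keeping it secondary.

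The cost is wording and figures in one section, with no extra patients and no change to tests or hierarchy. If the 25% applies to reached cases, the stated per-stratum power becomes less favourable.

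### Does describing the intention-to-treat groups as activated versus not activated leave the primary comparison undefined?

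*SAP*

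**What the plan says.** SAP section 3 states the analysis set in one sentence, which gives the principle and the groups together: "intention-to-treat principle (patients for whom the HeartRunner system was activated vs. not activated), except for cases excluded". The exclusions meant are those of protocol subsection 4.6. The sentence before it points to the third version of the protocol: "Eligibility, allocation, inclusion and exclusion are displayed in a trial diagram (Figure 1) and described in section 4 Study Methods in the study protocol version". So allocation is defined in the protocol, and the SAP relies on that definition.

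Everything later in the SAP uses the same two groups. The primary Fisher's exact test is there to "test whether activating the citizen responder system can improve 30-day survival". The combined analysis of strata 1 and 2 is a "logistic regression with intervention (yes, no) and time (<3 and 3-9) as fixed effects". The subgroup model in section 5 is similar: "A logistic regression with intervention (yes, no), subgroup and the interaction between intervention and subgroup will be used". The text around that model explains the intervention as activation of citizen responders.

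The outcome in section 1 is "30-day survival in OHCA patients included in the HeartRunner trial", so suspected arrests that prove not to be arrests fall outside the analysis. Section 2 expects this: "Data from the pilot study showed approximately 64% of suspected OHCA were real OHCA".

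**The concern.** The name of the principle and the description of the groups do not say the same thing. Intention-to-treat means analysis as allocated. Whether the system was activated is something observed after allocation. A programmer could take the arm from an activation flag in the dispatch data and claim to follow the SAP, while another could take it from the allocation record and claim the same. The available text has no other sentence that defines the groups, and none that places a case allocated to activation but not activated, or a control case that was activated.

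If such cases exist and their prognosis differs from the rest, grouping by activation breaks the randomised comparison. The risk difference can then be biased in either direction, and the primary test can reject too often when activation has no effect. The combined and subgroup regressions would carry the same error.

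**Working it through.** **1. The plan's own figures.** Inputs from SAP section 2: 15% versus 25% survival, two-sided alpha 0.05, power 0.80, Fisher's exact test. The available text does not state the allocation ratio; 1:1 is assumed.

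- Exact Fisher power at 268 per arm (536 in total) is 80.2%, so 536 reproduces.
- 536 / 0.64 = 837.5, stated as 838.
- 837.5 / 0.40 = 2093.75, stated as 2094.

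None of these depends on how the analysis groups are worded.

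**2. What the sentence most likely means.** Three places bear on it.

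- The sentence itself names intention-to-treat, which already fixes grouping by allocation.
- The preceding sentence refers the reader to the trial diagram and protocol section 4 for allocation.
- Section 5 treats intervention and activation as the same thing.

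Read together, the brackets say which two arms are compared. They also have a plausible use. Section 2 says that a responder reached the scene before EMS in only about 40% of activated cases. Defining the group by activation tells the analyst to keep the other 60% or so in the intervention arm, which guards against an as-treated analysis by arrival. The protocol change log fits this: it drops the subgroup based on arrival before EMS because arrival cannot be assessed in controls.

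**3. What the literal reading could cost.** The documents give neither a rate of cases handled against allocation nor their survival, so all of this is assumption. Take one stratum:

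- true arrests: 2094 × 0.64 = 1340, or 670 per arm;
- no true effect, 15% survival in each allocated arm, so 0.15 × 670 = 100.5 expected survivors per arm;
- m intervention cases not activated and counted as controls: 2%, 5% or 10% of 670, rounded to 13, 34 or 67;
- survival s in those cases of 30%, 15% or 5%.

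Expected survival under the literal grouping:

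- intervention = (100.5 − m·s) / (670 − m)
- control = (100.5 + m·s) / (670 + m)

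For m = 67 and s = 0.30: 80.4 / 603 = 13.3% and 120.6 / 737 = 16.4%, a difference of −3.0 points. For m = 67 and s = 0.05: 97.15 / 603 = 16.1% and 103.85 / 737 = 14.1%, a difference of +2.0 points.

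Rejection rates come from enumerating all outcomes of the two-sided Fisher test (p ≤ 0.05). The control count is the sum of a binomial (670, 0.15) and a binomial (m, s).

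| Survival of moved cases | Moved | Spurious difference (points) | Rejects | Rejects in favour of activation |
|---|---|---|---|---|
| 30% | 2% | −0.6 | 5.5% | 1.1% |
| 30% | 5% | −1.5 | 11.3% | 0.3% |
| 30% | 10% | −3.0 | 32.6% | 0.02% |
| 15% | 2%, 5%, 10% | 0 | 4.6% | 2.2% to 2.3% |
| 5% | 2% | +0.4 | 4.9% | 3.5% |
| 5% | 5% | +1.0 | 7.6% | 7.0% |
| 5% | 10% | +2.0 | 16.7% | 16.5% |

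Grouped by allocation, the same scenarios reject in about 4.1% of trials, about 2.1% in favour of activation. Simulation with 20,000 trials per scenario agrees within Monte Carlo error (32.6% and 16.5% in the two extreme 10% rows).

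**4. Reading the table.** With no case handled against allocation, the two groupings are identical. At 2% the rejection rate stays close to nominal. If the moved cases have average survival, there is no bias at any rate. When they have better survival, nearly all the excess rejections go against activation, so in a superiority trial a false claim of benefit becomes less likely. Only markedly poor survival in the moved cases makes a false benefit more likely.

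**The case for a change.** The strongest case for a change is that a primary-analysis rule should admit only one reading, and that correcting the clause would cost almost nothing. The words do describe what happened to the patient, the available text nowhere says that activation always followed allocation, and at 5% to 10% moved with a different prognosis the error would be material. All of that stands as a comment on drafting.

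It does not show that the planned analysis is wrong. The literal reading contradicts the principle named in the same sentence, so an analyst would have to set that principle aside to reach it. The apparent lack of any other definition partly reflects what is available: protocol section 4, subsection 4.6 and the diagram, to which the SAP refers, are not in the public text, where the protocol appears only as a change log. They may settle the point. If subsection 4.6 removed cases because they were not activated, that would be a separate question, and it cannot be judged here.

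Two related requests add little. Calling the set modified intention-to-treat changes no result, because the SAP already states its exclusions and limits the outcome to true arrests. Such a restriction is acceptable if confirmation of arrest does not depend on allocation. Counts by arm largely repeat what the planned trial diagram, which covers allocation, inclusion and exclusion, would be expected to show.

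**Conclusion.** No change is called for. The brackets are loose shorthand for the two arms, and the named principle tells the analyst what to do with a case not handled as allocated: keep it where it was allocated. An analysis run that way is sound, and 536, 838 and 2094 stay as they are.

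The possible harm is conditional. It requires analysts to follow the brackets instead of the principle, a real share of cases handled against allocation, and a different prognosis in those cases. On the assumptions used (1:1 allocation, 15% survival, no true effect, movement from intervention to control only), the spurious difference ranges from −3.0 to +2.0 points when up to 10% are moved, against a planned effect of 10 points. At 2% it is within about 0.6 points. Nothing in the available text suggests which rate, if any, applies.

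### Injury and stress are summarised only among activated responders, so the safety table cannot show the risk to those who set out or attend, and probably understates it

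*SAP*

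**What the plan says.** SAP section 1 lists two safety outcomes: "Physical injuries or accidents among activated citizen responders" and "Psychological stress or anxiety among activated citizen responders". On data collection it says: "Physical injuries and psychological stress will be assessed through an electronic survey sent out 90 minutes after activation". On missing answers: "Non-responders will be followed up by phone call, text message or e-mail".

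The analysis is the single sentence in SAP section 3: "The safety outcomes physical injuries and psychological distress and anxiety among the activated citizen responders will be presented by frequency distributions (number, percentages").

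SAP section 2 reports two pilot figures: "approximately 64% of suspected OHCA were real OHCA", and "in approximately 40% of cases for which the HeartRunner system was activated, at least 1 citizen responder arrived prior to EMS". It uses both to inflate the efficacy sample size.

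SAP section 6 names serious injury and psychological stress among responders as events for the monitoring board. It says of the research computer linked to the mission server: "Using this system, responses can be tracked continuously". It plans no safety analysis by response status.

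The supplied text does not define what activated means for an individual responder. Nor does it say whether the percentage is taken over all activated responders or over survey answers, or whether the unit is a person or an activation.

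**The concern.** The plan treats exposure differently for efficacy and for safety. For efficacy, section 2 accepts that an activation may not be a real arrest and may not bring a responder ahead of EMS, and it raises the sample size accordingly. For safety, a volunteer who did not move and one who performed resuscitation contribute equally to one percentage.

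Two readers need the risk given attendance: a volunteer deciding whether to go, and a board judging harm. A pooled percentage could support a statement that injury and stress are rare while the rate among those who attend is higher, and the planned table could not reveal this. With denominator and unit unstated, two analysts could also report different rates from the same data.

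**Working it through.** **The plan's own figures.** The documents state no safety rate and no safety sample size. The 64% and 40% enter only the efficacy calculation in SAP section 2, which reproduces:

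- 15% versus 25%, two-sided Fisher's exact test, alpha 0.05, 268 per arm (536 in total): exact power 0.802, against a target of 0.80.
- 536 / 0.64 = 837.5, stated as 838.
- 536 / 0.64 / 0.40 = 2093.75, stated as 2094.

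The plan therefore uses the two proportions consistently, as proportions of cases.

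**Dilution formula.** Let r be the risk among exposed responders, f the share of activated responders who are exposed, and q the risk in the others relative to r. Then

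- pooled rate = r × [f + q(1 − f)]
- understatement factor = r / pooled rate = 1 / [f + q(1 − f)]

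**Inputs.** The documents give neither f nor q at responder level. The case-level figures are borrowed for f only as an illustration: 0.64, 0.40, and their product 0.64 × 0.40 = 0.256. The product assumes independence. Without that assumption the joint share of cases could lie anywhere from 0.64 + 0.40 − 1 = 0.04 to 0.40. The values of q are assumptions.

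| f (assumed) | q = 0 | q = 0.5 | q = 1 |
|---|---|---|---|
| 0.64 | 1/0.64 = 1.6 | 1/0.82 = 1.2 | 1.0 |
| 0.40 | 1/0.40 = 2.5 | 1/0.70 = 1.4 | 1.0 |
| 0.256 | 1/0.256 = 3.9 | 1/0.628 = 1.6 | 1.0 |

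For scale, with an assumed r of 1% and q = 0, the pooled rate would be 0.64%, 0.40% or 0.26%.

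These factors are not bounds. With a purely assumed f of 0.10 the factor is 10 at q = 0 and 1/0.55 = 1.8 at q = 0.5. At q = 1 there is no dilution at any f.

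**The case against.** The strongest reply is that the planned measure is legitimate. Risk per activation is the volunteer-side counterpart of the activated-versus-not comparison used for efficacy. Counts are reported as well as percentages, and a denominator cannot dilute a count. The board sets its own guidelines and can receive reports from continuous tracking, so nothing ties it to the section 3 summary. All of this stands. It is why the all-activated figure should stay, and why this is a reporting gap rather than an error.

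A reader might go further and infer that most activated responders never reach a real arrest, or that risk is understated 3.9-fold. The documents support neither:

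- The 64% and 40% are shares of cases, not of responders.
- The 40% counts cases in which at least one responder came before EMS. It does not count everyone who came, and arriving after EMS is still attending.
- The factor of 3.9 needs independence, one responder per activation, and no risk at all in everyone else.
- If activated means accepted rather than alerted, much of the dilution disappears.
- If the denominator is survey answers, selective non-response could move the rate either way.

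Nor does the argument fit both outcomes equally. An accident can happen on the way, whether or not the case is a true arrest and whoever arrives first. A safety conclusion based only on scene arrivals would lose those injuries.

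Finally, only the change list of protocol version 3 was supplied, so a definition or breakdown in its methods sections cannot be ruled out.

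**Conclusion.** The concern holds in a limited form. One pooled percentage cannot show the risk to responders who set out or attend. It understates that risk if some activated responders do neither and have lower risk, which is likely for injury in transit or at the scene and for stress from a resuscitation. The size is unknown. The illustrative factors of 1.0 to 3.9 use case-level shares in place of a responder-level share, with assumed values for the risk in the others.

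This is a cheap improvement to a descriptive safety outcome. No test, sample size or primary result depends on it.

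**What to change.** In SAP section 3:

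1. Define activated for an individual responder. Keep the all-activated figure, and state its denominator (all activated or survey answers) and its unit (person or activation).
2. Beside it, report each safety outcome for responders who (a) accepted or set out, (b) reached the scene, and (c) reached a true cardiac arrest, with arrival before EMS shown separately.
3. Count injuries on the way in (a), and do not rest injury conclusions on scene arrivals alone.
4. Give the survey response rate after follow-up.

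The existing response tracking and the 90-minute survey should supply the data. If they do not record setting out or scene arrival, one added survey item would. The cost is SAP wording and a few extra table rows. The downside is smaller denominators, wider intervals where these are given, and percentages that will probably look less favourable.
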